Lessons on Urethral Lidocaine in Urodynamics ("LULU"): Impact of intraurethral lidocaine on cystometric parameters and discomfort, a RCT

NCT04038099

11/22/2019

Lessons on Urethral Lidocaine in Urodynamics ("LULU"): Impact of intraurethral lidocaine on cystometric parameters and discomfort, a RCT

Abstract

Complex cystometric studies are often conducted to assess for and clarify incontinence. In current practice, intraurethral aqueous jelly is used to lubricate and insert urethral catheters for these studies. Patients commonly complain of urethral discomfort and/or pain with catheter insertion. Two percent lidocaine jelly has not been routinely used in practice for cystometric catheter insertion due to the unknown impact it may or may not have on complex cystometric parameters. Previous studies evaluating the use of 2% lidocaine jelly for office cystoscopy have not proven to consistently provide substantial relief of discomfort. However, a recent study using 2% lidocaine jelly for catheter insertion during complex cystometric evaluation did demonstrate significant relief of discomfort. Some studies have evaluated 2% lidocaine jelly use during complex cystometric evaluation in neurogenic populations, indicating a surprising increase in detrusor overactivity with 2% lidocaine jelly use. However, few studies have evaluated the impact of 2% lidocaine jelly in a non-neurogenic population. If use of 2% lidocaine jelly was found to improve discomfort during complex cystometric studies in this patient population without substantially altering the study's findings, this could impact clinical practice in an important way. Herein, we propose a randomized, double blind, controlled trial for patients undergoing complex cystometric evaluation. Patients will undergo routine complex cystometric evaluation for acquisition of baseline data using a small amount of intraurethral aqueous jelly for catheter lubrication. Then, they will be randomized to instillation of either placebo (additional intraurethral aqueous jelly, 5ml) or intraurethral 2% lidocaine jelly. Participants then undergo complex cystometry a second time. Normal variations in studies with placebo will be compared to variations within the 2% lidocaine jelly group to determine if

cystometric parameters are altered in any clinically important ways. Patient discomfort will also be evaluated by both the patient and the urodynamics advanced practice nurse.

Purpose of Study

This trial will assess whether use of intraurethral 2% lidocaine jelly meaningfully impacts sensation during filling (i.e., a change of more than 25% of first sensation, first desire to void, strong desire to void, or maximum cystometric capacity) and determine whether the use of intraurethral 2% lidocaine jelly meaningfully impacts pain/discomfort, filling metrics, and voiding metrics.

Hypothesis: In women without known voiding dysfunction being assessed for urinary incontinence by urodynamic studies (UDS), the use of intraurethral 2% lidocaine jelly during cystometry and pressure flow study (PFS) will not meaningfully impact sensation during filling and will decrease discomfort for patients.

Significance of the Study

Patients often complain that urodynamic bladder testing is uncomfortable and even painful, for some. Intraurethral lidocaine 2% jelly has been used to demonstrate increased patient satisfaction with comfort during this procedure. However, the effect of intraurethral lidocaine jelly on urodynamic test results has not been fully studied. Considering that lidocaine jelly is a local anesthetic, it may have a numbing effect, potentially increasing time to first sensation and bladder capacity, decreasing ability to empty the bladder, and may potentially mask detrusor overactivity (DO). However, if the local anesthetic has no effect on urodynamic test results, one may consider changing practice to include intraurethral 2% lidocaine jelly with urodynamic testing to improve patient satisfaction and comfort.

Background of the Problem

Standard teaching for the performance of UDS is that after completion of the uninstrumented uroflowmetry, cystometry is completed using plain intraurethral aqueous jelly for insertion of the transure thral pressure catheter. Clearly, this can be a source of discomfort and pain for the patient. An alternative to plain lubricant, such as 2% lidocaine ielly, may relieve discomfort for patients but could theoretically impact or distort important cystometry findings, e.g., first or strong sensation and presence/absence of DO. Further, voiding could be affected if numbing the urethra blunts sensory nerves that serve to amplify bladder contractions and maintain efficient bladder emptying.(1, 2) A recent study of healthy volunteers randomized to intraurethral aqueous jelly versus 2% lidocaine jelly did not identify any detriment to voiding efficiency using lidocaine but did find greater interrupted flow patterns and more electromyography (EMG) activity during micturition when using lidocaine.(3) This study found no difference in pain perception between groups. Similarly, a meta-analysis of 9 randomized trials assessing lidocaine jelly versus plain jelly lubrication for office flexible cystoscopy did not suggest a significant difference in the efficacy of pain control using lidocaine.(4) Conversely, a different trial that compared water-based lubricant and 2% lidocaine jelly for UDS in women did find substantially less pain for patients using the lidocaine jelly.(5)

Neither of the above two trials of UDS in women compared participants *to themselves* to determine how filling and voiding metrics may change before/after lidocaine jelly was applied. It remains uncertain whether these parameters would change in clinically meaningful ways with the addition of lidocaine, and the possible benefit of lidocaine—i.e., decreased discomfort for the

patient—has not been definitively proven or disproven. Using patients as their own controls, this proposal aims to determine if the use of intraurethral 2% lidocaine jelly during cystometry and pressure flow study impacts filling and emptying measures while assessing patient discomfort at various time points during their procedures.

One prior study utilizing patients as their own control evaluated patients with urgency but no urge incontinence and reported DO on a repeat cystometry after no DO was observed on initial cystometry, indicating that lidocaine jelly may increase DO. (6) Additional studies have explored the effect of intravesical lidocaine on cystometric results within neurogenic populations, but few studies to date have looked at the effect of lidocaine jelly on cystometric parameters and DO in the normal population of patients with incontinence in the absence of neurogenic disease.

Methods & Analyses:

Urodynamic testing will be performed in procedure rooms by qualified advanced practice nurses in the field of female pelvic medicine and reconstructive surgery (FPMRS). Eligible patients meeting inclusion criteria will be consented for study participation prior to urodynamic testing. Standard urodynamic testing will be conducted, i.e., first un-instrumented uroflowmetry, then cystometry (including leak point pressure assessments, LPP) and a pressure flow study (PFS) with 1-2ml of aqueous jelly in the urethra. UDS will be completed with a dual-sensor 7-Fr catheter inserted through the urethra into the bladder and a second 7-Fr catheter in the vagina. Patch electrodes will be adhered peri-anally in the standard fashion for EMG. Patients will be filled with room-temperature sterile water at 60mL/min. Volumes at first sensation, first desire to void, strong desire to void, and maximum cystometric capacity will be recorded. Presence or absence of DO during cystometry will be documented. Other measures (detailed below) will be recorded during cystometry and PFS. After the patient voids for her first PFS, she will be

randomized (1:1) to either additional water-based lubricant (placebo) or lidocaine 2% jelly (5mL).

Randomization will be stratified by presence/absence of DO on the initial cystometry. A balanced randomization scheme will be generated with equal numbers of placebo and lidocaine. Identically appearing study drug syringes will be placed in consecutively numbered opaque envelopes by an unmasked study coordinator not participating in the procedure visit or study analyses. Both the urodynamic nurse and patient will be blinded to the type of lubricant. After randomization, the urethral catheter will be removed and 5mL of either placebo or 2% lidocaine will be injected into the urethra. The patient will sit for 5 minutes to allow lidocaine to take anesthetic effect. The catheter is then replaced, and cyostometry and PFS will be repeated. A continuous pain scale from 0 to 100 (visual analog scale) will be used by the patient to report her pain level during cystometry #1 (during catheter insertion and at maximum cystometric capacity), PFS #1, overall UDS #1, cystometry #2 (during catheter insertion and at maximum capacity), PFS #2, and overall UDS #2 discomfort. At the end of the procedure, the urodynamic nurse will also provide a subjective assessment of patient discomfort.

Planned Analyses & Power Calculation:

The primary outcome is the volume at which a participant perceives a strong desire to void. Statistical analyses will estimate the confidence interval for this outcome measure between the two arms of the study (i.e., using 2% lidocaine vs. aqueous jelly) through the standard calculation for the difference in means when standard deviations of the two arms are unknown, i.e., through the Student's t distribution. As it is thought that there will be no difference in the mean value of the two arms, the study will be designed as an equivalence trial. Since DO may alter findings, it is planned to stratify the randomization for DO in order to insure a balance between the arms for this variable. Prior to randomization, each patient will undergo a

baseline standard cystometry without lidocaine, and DO (present or absent) will be obtained from this evaluation. The observations from this *baseline cystometry* provide for an interesting and novel analysis: the baseline measure of volume at strong desire to void may serve as a covariate to adjust for individual patient variability. That is, comparisons of the difference in the baseline measure and the experimental measure will provide a patient "standardized" evaluation of her additional volume following the baseline. Analysis of the primary outcome will account for patient variability with standardization by the value of the baseline measure.

Beyond the primary outcome cystometric evaluations are numerous secondary outcomes such as pain/discomfort with filling and emptying, presence/absence of DO, and emptying metrics including flow rates, post-void residual, EMG activity, and detrusor pressures (max and at peak flow). Continuous measures will use the Student's t distribution as with the primary outcome. Binary and ordinal outcomes will be evaluated using logistic regression. The use of logistic regression for the ordinal outcomes is through the proportional odds model and combines with the cumulative logit link. All of these evaluations may incorporate the baseline urodynamic study metrics as a covariate (as described above for the primary outcome).

Assuming an average strong desire to void during cystometry (with plain lubricant gel) of 300mL, standard deviation of 100mL (3, 5), a non-inferiority margin of 75mL (i.e., 25% of 300mL), Power (1- β) of 0.80 and α of 5%, **31 participants per study arm** (i.e., 62 total) are needed to demonstrate "equivalence" in sensation during cystometry using plain lubricant gel versus lidocaine gel. Allowing for 12% participants being unable to complete the second half of the UDS, a total of **35 participants per study arm** (i.e., **70 total participants**) will be enrolled.

In the placebo group, the data from the two filling cystometry tests can be compared (sensation metrics, DO presence/absence, and compliance) to establish "normal variability". Anecdotally, patients commonly tolerate a second fill better. With this normal variability better

defined, we will be able to assess for changes attributable to the lidocaine in the group receiving the anesthetic jelly—specifically, whether volume of first sensation or bladder capacity is altered. We can also assess lidocaine's impact on bladder emptying by comparing voiding metrics. In patients with repetitive DO on their first cystometry, we will be able to assess whether they continue to demonstrate DO on their second cystometry with lidocaine.

Primary Outcome: Assess whether use of intraurethral 2% lidocaine jelly meaningfully impacts sensation during filling (specifically, strong desire to void).

Secondary Outcomes: Determine whether the use of intraurethral 2% lidocaine jelly meaningfully impacts the following:

Pain/ Discomfort

- 1. Measured by a visual analog scale during cystometry (catheter insertion and at maximum cystometric capacity), during PFS, and post-procedure
- 2. Provider perception of patient discomfort

Filling Metrics (besides sensation)

- 3. Presence/ absence of detrusor overactivity (DO)
- 4. Compliance ($\Delta Volume / \Delta P_{det}$)

Voiding Metrics

- 5. Maximum flow rate (mL/sec)
- 6. Voiding pattern: normal, intermittent, interrupted
- 7. Detrusor void (yes/no) vs. Valsalva vs. mixed void
- 8. Voided volume and post-void residual (mL)
- 9. Voiding efficiency, i.e., voided volume/ (voided volume + PVR) (3)

- 10. P_{det}max (cm H₂O)
- 11. P_{det}peak flow (cm H₂O)
- 12. EMG activity

Participant Eligibility

Inclusion Criteria	Exclusion Criteria
Female patients	Diagnosis of pelvic pain, interstitial cystitis, or bladder pain syndrome
>18 years of age	Known neurogenic disease impacting voiding/ continence (e.g., Parkinson disease, multiple sclerosis, myasthenia gravis, recent stroke)
Already scheduled (or being scheduled) for UDS to assess urinary incontinence	Active UTI
Able to speak and read in English	Pelvic organ prolapse that is unable to be easily reduced
	Pregnancy or breastfeeding
	Allergy or hypersensitivity to lidocaine or local anesthetics

Ethical Conduction

The study site will have a principal investigator and study coordinator, both skilled in conduct of IRB-approved clinical research, responsible for obtaining and appropriately documenting informed consent of each patient before beginning any study related procedure. Once patients have completed informed consent and have enrolled, each participant will be assigned a Participant ID that is an anonymous patient study number. Only the research coordinators and the site PI will have access to the list linking medical record number to participant ID. A research coordinator not involved in the care of the patient will have knowledge of whether a patient received lidocaine jelly or placebo (water based lubricant). The research coordinator and site PI will have the responsibility for securing original source documents containing any identifiable patient data. Each patient's study documents will be kept

under an individual tab in a binder, and the binder(s) will be stored in a locked cabinet and office. All information collected about the subject during the course of this study will be kept confidential to the extent permitted by law. Besides the specified study team, other access to study records or data would only be by the IRB or the study sponsor (SUNA) at their request. All information the subject has provided will be kept in a research record and stored in a locked office and on a secure, password protected computer. Research information will not be made a part of the participant's regular medical record. There is no personal information (name, social security number, etc.) about the subject that is associated with subject's research data; a Participant ID number will indicate a subject's identity on the research records. Patients routinely are escorted to exam rooms alone, but they may choose to have a family member or spouse present if that is her preference. The informed consent and the history and exam findings will be collected in a private room. The informed consent will be written and provided in English. Either the research coordinator or another member of the research team (PI or coinvestigator) will be obtaining the consent, and the patient will sign and date/time her name to indicate understanding, which will be observed and countersigned by the person obtaining the consent. No matter what position of authority a research member has, the subject will be assured of the right to refuse to participate and/or the right to withdraw at any point in the study. The urodynamics nurse will be trained to minimize discomforts during the procedure.

A patient's Participant ID number will be provided to the central data collecting center (UTSW) with no personal information. Further, data will be entered using REDCap, a Webbased, HIPAA-complaint tool used by many major medical institutions. REDCap facilitates electronic form building and data collection. It has an automatic audit trail, report builder capability and data quality module. REDCap can export data to SAS, SPSS, R, STATA, or Microsoft Excel. The REDCap database will reside on a secure UTSW server with continuous backup. Only authorized personnel with designated rights can access this study, and that at

various levels. For example, a coordinator will be able to enter and check data, but cannot design screens. REDCap provides a protocol event schedule where specific forms are linked to events (visits) in the protocol. Authentication used in the REDCap application is compliant with the UT Southwestern Medical Center's Health System password and security standards.

Project Timeline

Research Task	Projected Time Course
Completion of IRB application, site review, project start-up processes, registration with clinicaltrials.gov	3 months
Participant recruitment, data collection (anticipating 5-6 procedures/ month)	12 months
Data analyses	1 month
Manuscript preparation/ submission/ edits, SUNA presentation preparation, final data entry in clinicaltrials.gov	2 months
TOTAL	18 months

Study Budget

Please see appendix A. Given that we will be conducting a 2nd CMG and PFS on patients already having urodynamic studies performed, we will not need any additional supplies other than the randomized jelly syringes. A registered nurse will prepare blinded jelly syringes of lidocaine vs. aqueous jelly solution. Research coordinator/urodynamicist time is included in the study budget. Salary support includes time for the nurse practitioner and/or physician(s) to submit to the IRB, VELOS, clinicaltrials.gov, and data entry within REDCap system, as well as time for consenting patients and performing additional complex cystometrogram with pressure flow study. It is estimated that the consent process and additional procedure time will be roughly 150 hours for 70 patients over the course of 12 months. Additional data entry support may be required, and this is calculated in the budget, as well.

Research Environment

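### Equivalence on strong desire to void supports a conclusion about that volume only, while the stated hypothesis covers four filling volumes

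*Combined protocol and SAP*

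**What the plan says.** - **Definition and hypothesis (Purpose of Study).** A meaningful effect on sensation is "a change of more than 25% of first sensation, first desire to void, strong desire to void, or maximum cystometric capacity". The hypothesis then says that lidocaine will have no meaningful effect on filling sensation, without limiting this to one volume.
- **Why these volumes matter (Significance; Background).** Lidocaine is described as "potentially increasing time to first sensation and bladder capacity", and an alternative lubricant "could theoretically impact or distort important cystometry findings, e.g., first or strong sensation and presence/absence of DO". The Significance section adds that "if the local anesthetic has no effect on urodynamic test results, one may consider changing practice".
- **Data (Methods & Analyses).** "Volumes at first sensation, first desire to void, strong desire to void, and maximum cystometric capacity will be recorded".
- **Primary outcome (Planned Analyses & Power Calculation; Primary Outcome).** "The primary outcome is the volume at which a participant perceives a strong desire to void". The Primary Outcome statement also narrows sensation to strong desire. The power calculation gives a mean of 300 mL, an SD of 100 mL, a margin of 75 mL, power 0.80, alpha 5% and 31 per arm, all for this volume.
- **The other three volumes.** The Abstract says "Normal variations in studies with placebo will be compared to variations within the 2% lidocaine jelly group to determine if" the cystometry readings change in a clinically important way. Planned Analyses foresees comparing sensation metrics between the two placebo fills, and asking whether first sensation or bladder capacity is altered. For secondary outcomes, "Continuous measures will use the Student's t distribution as with the primary outcome". The filling group in the Secondary Outcomes list expressly leaves out sensation and contains only detrusor overactivity and compliance.

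**The concern.** The definition is joined by *or*, so a change beyond 25% in any one of the four volumes is a meaningful effect. To support the hypothesis of no such effect, all four must be shown to stay within 25%. The analysis plan sets up that demonstration for one of them.

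At stake is what the trial can conclude. The plan itself names first sensation and bladder capacity as findings that lidocaine might shift, and it links a possible change of practice to the absence of any effect on test results. With strong desire within 75 mL, a report could say that filling sensation is not meaningfully affected although nothing had been shown about the other volumes against the plan's own criterion.

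**Working it through.** **1. Reproduce the plan's figure.** Inputs from Planned Analyses & Power Calculation: SD 100 mL, margin 75 mL, power 0.80, alpha 5%. With two one-sided 5% tests and a true difference of 0:

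n per arm = 2 × [SD × (z0.95 + z0.90) / margin]² = 2 × [100 × (1.645 + 1.282) / 75]² = 30.45, rounded up to 31.

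This matches the plan. At 31 per arm the exact t-based power is 0.797. Two one-sided 5% tests correspond to a 90% confidence interval. With a 95% interval, power at 31 per arm would be about 0.66. The plan states no interval level, but its sample size implies 90%.

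**2. Set the four volumes side by side.**

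| Volume | In the 25% definition | Recorded | Listed outcome | Reference mean, SD, mL margin | Comparison foreseen |
|---|---|---|---|---|---|
| First sensation | yes | yes | no | none | yes, named |
| First desire | yes | yes | no | none | only within sensation metrics |
| Strong desire | yes | yes | primary | 300, 100, 75 mL | equivalence |
| Maximum capacity | yes | yes | no | none | yes, named as bladder capacity |

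The hypothesis needs the second column. The equivalence analysis covers one row.

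**3. Does the sample size carry over?** Dividing by the mean, a 25% limit needs n = 2 × [CV × 2.927 / 0.25]² per arm.

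- CV 0.33 (strong desire's own 100/300): 31 per arm.
- CV 0.40: 2 × 4.683² = 43.9, so 44.
- CV 0.50: 2 × 5.854² = 68.5, so 69.

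At 31 per arm without baseline adjustment, t-based power is 0.80, 0.57 and 0.24 respectively. Baseline adjustment multiplies the SD by √(1 − ρ²), where ρ is the correlation between a volume's two fills. The largest CV that keeps power at 0.80 then rises from 0.33 to 0.38 (ρ = 0.5) or 0.47 (ρ = 0.7). The documents give no CV or ρ for the other three volumes, so these values are assumptions.

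**4. Power to place all four within 25%.** Simulated at 31 per arm with no true effect and 90% intervals. The strong-desire limit was 75 mL and the other limits were 25% of the observed pooled baseline mean. Ranges are over between-volume correlations of 0.3 to 0.7, also assumed.

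| CVs (first sensation / first desire / strong desire / capacity) | Unadjusted | ρ = 0.5 | ρ = 0.7 |
|---|---|---|---|
| 0.33 for all | 0.43–0.56 | 0.70–0.77 | 0.93–0.95 |
| 0.50 / 0.40 / 0.33 / 0.33 | 0.10–0.16 | 0.29–0.37 | 0.63–0.67 |

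In a simulation check, also holding strong desire to 25% of its own pooled baseline mean lowered these figures by about 0.01 at most.

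**5. Why strong desire needs both limits in the wider statement.** 75 mL is 25% only if the mean is 300 mL. If the observed mean were 200 mL (illustrative), 75/200 = 37.5%, so meeting 75 mL alone would not meet the 25% definition.

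**The case against.** The case for leaving the plan as it stands has several parts.

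- **One primary outcome among related measures is legitimate, and the Primary Outcome statement itself narrows sensation to strong desire.** This stands. It settles the primary analysis. It does not change the hypothesis, which is still worded over the four-volume definition.
- **The other volumes are not ignored.** This also stands. All four are recorded, and looking at first sensation and capacity is foreseen. A reader might infer that these volumes go unanalysed, and the documents do not support that. What is missing is outcome status and any use of the 25% limit. Asking whether a volume is altered is not the same as showing that it stays within a limit.
- **The 25% is a relative limit and the conversion to mL is shown once, so it could be repeated.** It could, and the fix does so. The plan does not say that it will be, or from which mean.
- **No rule says that strong desire alone may carry the wider claim.** True. No rule prevents it either, and the hypothesis as worded invites it.

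A stronger reading is that the trial will take a non-significant t-test on these volumes as proof of no change. The documents do not support this. The primary analysis is a confidence interval from the t distribution, secondary continuous outcomes follow the same method, and no significance test is said to be read that way.

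**Conclusion.** The concern holds as a mismatch between what the hypothesis covers and what the equivalence analysis can show. Equivalence within 75 mL on strong desire supports a conclusion about strong desire. It does not support the hypothesis over all four volumes. This follows from the text and rests on no assumed figure.

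A reader might infer that the primary outcome, margin or sample size is wrong. None of these is: 31 per arm reproduces from the plan's own inputs.

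How hard the wider statement would be to support cannot be known from the documents, which give no means, SDs or correlations for the other three volumes. Without baseline adjustment, and with strong desire's CV for all four, joint power is about 0.4 to 0.6. It is lower with larger CVs and higher with baseline adjustment. These figures are illustrative and do not measure harm.

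**What to change.** 1. Confine the hypothesis and the confirmatory equivalence conclusion to strong desire to void. Leave the 75 mL margin and the sample size as they are.
2. Add first sensation, first desire and maximum cystometric capacity to the Secondary Outcomes. Report each between-arm difference with the same baseline adjustment as the primary outcome and a 90% confidence interval, set against 25% of that volume's mean at the first cystometry, pooled over both arms.
3. Do not state that filling sensation as a whole is free of meaningful effect unless all four intervals lie within 25% of their own pooled first-cystometry means. For this statement, strong desire must meet that limit as well as 75 mL. Requiring all four does not inflate the type I error.
4. State that the trial is powered for strong desire only, so an interval crossing a limit may reflect imprecision and not an effect.

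**Cost.** Changes to the hypothesis and outcome list, three further interval analyses and one reporting rule. All four volumes are already collected, so no patients or procedures are added. The downside is that the wider statement becomes harder to make, with a joint power that cannot be fixed in advance from the documents. The strong-desire conclusion is unaffected.

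### Baseline detrusor overactivity (DO) is the stratification factor, but the primary model does not name it, the second-fill DO model makes baseline terms optional, and new DO in DO-negative women has no stated analysis

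*Combined protocol and SAP*

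**What the plan says.** **Randomization.** Under Methods & Analyses: "Randomization will be stratified by presence/absence of DO on the initial cystometry". Planned Analyses & Power Calculation gives the reason: DO could affect the findings, so the arms should be balanced on it.

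**Primary analysis.** The same section compares mean volume at strong desire to void between arms using Student's t distribution. It proposes the first-fill value of that volume as a covariate and also describes a difference from baseline. Baseline DO is not named.

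**DO as an outcome.** Presence or absence of DO is secondary outcome 3. "Binary and ordinal outcomes will be evaluated using logistic regression", and "All of these evaluations may incorporate the baseline urodynamic study metrics as a covariate". The second sentence permits adjustment but does not fix it.

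**Fill-to-fill change.** The Abstract says that variation under placebo will be compared with variation in the lidocaine group. Planned Analyses & Power Calculation adds that in the placebo group "the data from the two filling cystometry tests can be compared (sensation metrics, DO presence/absence, and compliance) to establish" normal variability, and then that "we will be able to assess for changes attributable to the lidocaine in the group receiving the anesthetic" jelly. The clause that follows singles out first sensation and bladder capacity, not DO. A further sentence says that women with repetitive DO on the first fill can be assessed for continued DO on the second fill with lidocaine.

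**Why DO matters to this trial.** Background of the Problem says an alternative lubricant "could theoretically impact or distort important cystometry findings, e.g., first or strong sensation and presence/absence of DO". Significance of the Study raises masking of DO as a possibility. Background also cites one study, in patients with urgency but no urge incontinence, that "reported DO on a repeat cystometry after no DO was observed on initial cystometry".

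**The concern.** A factor thought important enough to stratify on normally goes into the analysis model. If it is left out, the variation between strata stays in the residual although the design has removed it from the arm comparison. The standard error is then larger than it needs to be. Here the omission affects the primary model, and possibly the DO model, where adjustment is left to choice.

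The second issue concerns DO as a result. Masking can occur only in women with DO on the first fill, and new DO only in women without it. These groups are the two randomization strata. One odds ratio for second-fill DO, even with baseline DO as a main effect, does not show which way individual women changed. What is at stake is how the DO result is described, not the primary conclusion.

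**Working it through.** **1. The plan's own figure.** The inputs from Planned Analyses & Power Calculation are margin 75 mL, SD 100 mL, power 0.80 and alpha 5%. For equivalence by two one-sided 5% tests with true difference 0:

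n = 2 × [100 × (1.645 + 1.282) / 75]² = 30.45, rounded up to 31 per arm.

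This matches the stated 31. The calculation makes no use of baseline volume or DO, so nothing below changes the sample size.

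**2. Primary model: cost of omitting DO.** The documents give no DO prevalence, DO effect on volume or fill-to-fill correlation, so these are assumed:
- prevalence p and first-fill volume reduction D: 30% and 50 mL, 40% and 80 mL, 50% and 100 mL;
- first-fill total SD 100 mL;
- within-stratum correlation ρ between fills: 0.3, 0.5, 0.7;
- reduction on the second fill D₂: equal to D, D + 30 or D − 30 mL.

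Let b = p(1 − p) and within-stratum variance w = 100² − bD².

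*ANCOVA on first-fill volume:*
- residual variance with DO: w(1 − ρ²);
- residual variance without DO: (w + bD₂²) − (ρw + bDD₂)² / 100²;
- SE excess: square root of (without / with), minus 1.

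Example with p = 0.5, D = 100, ρ = 0.3, so w = 7500 and the variance with DO is 7500 × 0.91 = 6825:
- D₂ = 100: 10000 − 4750²/10000 = 7743.75; √(7743.75/6825) = 1.065, excess 6.5%.
- D₂ = 130: 11725 − 5500²/10000 = 8700; excess 12.9%.
- D₂ = 70: 8725 − 4000²/10000 = 7125; excess 2.2%.

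*Change score:* the variance with DO is 2w(1 − ρ); without DO, b(D₂ − D)² is added. An equal effect gives 0%. The largest case (p = 0.5, D = 100, ρ = 0.7) is √[(4500 + 225)/4500] = 1.025, excess 2.5%.

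Range over the whole grid:

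| Analysis | Equal DO effect | 30 mL larger on fill 2 | 30 mL smaller on fill 2 |
|---|---|---|---|
| ANCOVA | 0.5–6.5% | 4.1–12.9% | 0–2.2% |
| Change score | 0% | 0.7–2.5% | 0.7–2.5% |

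A separate simulation used a plain t-test at 31 per arm (20,000 trials; DO effect 25 to 100 mL; prevalence 30% or 50%). Without DO, type I error ran from 0.051 down to 0.029. Power was 0.80 to 0.86 without DO and 0.81 to 0.92 with it. The error of omission is on the safe side.

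**3. Second-fill DO: an illustration only.** All rates are assumed. Take 31 completers per arm, 12 DO-positive and 19 DO-negative on the first fill. Persistence is 75% on placebo and 45% on lidocaine; new DO is 10% and 30%.
- Second-fill DO: placebo 12 × 0.75 + 19 × 0.10 = 10.9; lidocaine 12 × 0.45 + 19 × 0.30 = 11.1.
- Status changed between fills: placebo 12 × 0.25 + 19 × 0.10 = 4.9; lidocaine 12 × 0.55 + 19 × 0.30 = 12.3.
- Odds ratios fitted to expected counts (Wald 95% CI): pooled 1.03 (0.36–2.91); with baseline DO as a main effect 1.03 (0.33–3.23); DO-positive stratum 0.27 (0.05–1.54); DO-negative stratum 3.86 (0.64–23.1).

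The cancellation depends on prevalence. With 6, 9, 12, 15 or 18 DO-positive women of 31, the pooled odds ratio is 1.68, 1.29, 1.03, 0.84 or 0.69. If only masking occurs it is 0.57 (0.19–1.72), and if only new DO occurs it is 1.66 (0.60–4.61).

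**4. Precision of the stratum estimates.** Rounding these counts, 5/12 versus 9/12 gives −33 points (Newcombe 95% CI −61 to +5), and 6/19 versus 2/19 gives +21 points (−5 to +45). Fisher power at the assumed rates is about 0.21 and 0.22.

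**The case against.** The strongest reply is that the plan already covers much of this. The Abstract commits to comparing placebo variation with lidocaine variation, the analysis section lists DO in that variability, and persistence of repetitive DO is mentioned. A reader might infer that no between-arm comparison of DO change is planned; the documents do not support that. The outline, however, gives no estimate, stratum or direction. Repetitive DO is narrower than the DO-present stratum, and new DO in DO-negative women has no analysis text.

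Stratifying for balance does not by itself oblige the trial to report stratum estimates. That is fair: DO is one of twelve numbered secondary outcomes, and the stated purpose is balance. The case for the table rests on the protocol's own interest in DO, not on the stratification.

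The offset example needs opposite effects of suitable size near one prevalence. That also stands. A reader might infer that the pooled odds ratio will hide a real effect; the protocol raises each direction separately and never says both will occur. In the one-direction cases the pooled estimate moves the right way.

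Finally, the primary-model gain is small. This is accepted, and the 12.9% upper end holds for only one sign of the 30 mL difference.

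**Conclusion.** The point holds as a modest improvement. Baseline DO should be a stated term in both models because it is the stratification factor and the plan itself expects it to matter. Under the assumed values, omitting it from the primary model inflates the standard error by 0.5 to 6.5% (ANCOVA, equal DO effect), by about 0 to 13% (ANCOVA, effect differing by 30 mL in either direction) or by 0 to 2.5% (change score). A reader might infer that the equivalence conclusion is at risk. It is not: the interval is somewhat too wide, which makes equivalence harder, not easier, to claim.

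The DO outcome needs a reporting clarification. A direction-specific tabulation by arm is unstated, most clearly for new DO in DO-negative women. The size of any loss there cannot be given, because the documents contain no DO rates.

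**What to change.** 1. In the primary model, include baseline DO (present or absent) alongside first-fill volume at strong desire to void.
2. In the logistic model for second-fill DO, make baseline DO a set term rather than an optional one.
3. Add one table of second-fill DO, lidocaine versus placebo: persistence in women with DO on the first fill (with the repetitive-DO subset as a row) and new DO in women without it. Give each an effect estimate and 95% CI, exact or penalized where counts are sparse. Label them descriptive.
4. State that a pooled odds ratio near 1 will not alone be taken as showing no effect on DO.

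The cost is one degree of freedom in each model and one table from data already collected. The sample size is unchanged. The stratum intervals will be wide and should be presented as such.
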